The research is significant because it will develop a new mHealth strategy to reduce skin cancer. In 2019, 5.4 million cases of keratinocyte cancers (basal and squamous cell)⁴ and 96,480 cases of melanoma will occur. Melanoma has doubled over the last 3 decades²² and will cause 7,230 deaths this year²³ (nearly as many deaths as due to drunk driving²⁴). Exposure to solar ultraviolet radiation (UV) is a primary cause,²⁵⁻³⁴ both lifetime UV exposure^{25-28,35} and intermittent, severe exposure (i.e., sunburn).¹⁵⁻²¹ The U.S. Surgeon General issued a *Call to Action to Prevent Skin Cancer*,¹⁶ citing its high prevalence⁴ and annual cost (\$4.8 bil. for non-melanoma skin cancer; \$3.3 bil. for melanoma³⁶). Its recurrence,³⁷⁻³⁹ and treatment disfigurement⁴⁰⁻⁴³ also prioritizes prevention. Primary prevention of skin cancer relies on reducing UV exposure by limiting time in the sun when UV is high (e.g., at midday; at lower latitudes; near summer solstice) and using shade, protective clothing, and sunscreen. But, people inconsistently take precautions,¹⁶ so efforts are needed to promote sun protection.⁴⁴⁻⁴⁶

3A.2. Correlation between Physical Activity and Skin Cancer

The research is significant because it seeks to improve sun protection among individuals engaged in physical activity, a beneficial health behavior that is also related to unprotected sun exposure and risk for skin cancer. Meeting guidelines for physical activity provides numerous positive health effects;⁴⁷⁻⁵¹ however, melanoma has a positive risk association with physical activity.¹¹ Physical activity is associated with sunburn,^{7,8,52-54} skin cancer risk behaviors,⁹ melanoma in both genders,^{11,55} and keratinocyte skin cancers, chiefly in men.^{56,57} It was estimated that sunburn is twice as likely to occur in physically-active than inactive people^{52,53} and is linked to aerobic activity (e.g., running and cycling).^{5,53} Cardiorespiratory fitness is related to an increased risk of melanoma⁵⁵ especially in high-UV locations, suggesting sun exposure plays a role.¹¹ In one study, persons who were more physically active were less concerned about sun exposure.⁵⁸ Together, the evidence implies that the behavioral phenotype of exercisers leads to increased UV exposure, elevating risk for developing skin cancer.

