In the two-year R21 research (see timeline in **Section 2.7. Form E**), we will conduct rigorous formative research and pilot-testing of the *Strava Sun* (SS) intervention. We will create study protocols in Month 1. Outdoor exercisers (Strava users and non-users) will give input on initial concepts for SS in focus groups during Months 2-5. An algorithm that predicts time of day and day of week exercising outdoors during high UV will be built using retrospective Strava user data in Months 6-8. In Months 9-15, a prototype of the SS database will be created and messages and delivery methods tested for usability/acceptability. In Months 16-21, feasibility of SS will be tested in a pilot field trial with Strava users. *While the many aims are to establish methodologic feasibility, analysis of the pilot field trial in Months 22-24 will test the hypothesis that SS will improve sun protection. To achieve the ambitious timeline, we will use protocols and methods developed in prior research (see Box 2 and 3).* All procedures will be approved by the Western Institutional Review Board.

3C.2. Target Population: Outdoor Exercisers on Strava

Target population will be users of the *Strava* social network. Inclusion criteria include a) being 18 or older, b) U.S. resident, c) engaging in regular physical activity outdoors (at least 156 times in past year [3 times per week]), and d) consenting. All participants except non-Strava users in focus groups will: e) be tenured *Strava* members (for 1+ full calendar year), f) upload at least 13 activites to *Strava* in past month (i.e., 3 per week), and g) give permission for us to access their activity data. *Strava* has 42 million members worldwide, providing a very large user population. *All recruiting, besides for focus groups, will occur by invitations through Strava (e.g., posting in clubs). Interested users will click a link to a study registration website. We cannot screen users based on inclusion criteria on Strava directly, so interested trial participants will complete a screener on the study website to determine eligibility. We expect participants to regularly participate in outdoor exercise, thus being a high-risk group, and to actively use Strava.*

3C.3. Formative Focus Groups (Specific Aim 1)

Four **focus groups** will be conducted with adults who engage in outdoor physical activity and use *Strava*, or not, in Colorado in Months 4-5 (compensation=\$50).

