Eight months are allotted for the field trial. Participants will be enrolled on a rolling basis and participate in *SS* for 4 months in the intervention condition. After pretesting, participants will receive sun protection messages from *SS* through emails/comments based on algorithm results from their profile and activity data (see **3C.4**). All participants will complete posttest survey 4 months after randomization. They will receive links to both surveys via email and text and complete them using KB's QuestionPro software. Surveys will contain measures of self-efficacy, response-efficacy, sun protection practices, sunburn (defined as skin red and/or painful from exposure to the sun in the past four months),⁹⁶ and barriers to sun protection from the *sunZapp* and *GSS* trials (see **Boxes 1** and **2**), recall of *SS* messages (i.e., times they read the notifications; preferred type of message), and acceptability of receiving *SS* messages in future. We will assess physical activity behaviors at both pre- and posttest, using the validated International Physical Activity Questionnaire (IPAQ)^{97,98} long form and current activity data uploaded by participants to *Strava*. Intervention participants will be compensated \$65 total (\$30 pretest, \$35 posttest) and control group participants \$45 total (\$20 pretest, \$25 posttest).

3C.7. Data Management and Analysis

Focus groups will be recorded, transcribed, and analyzed using *Atlas-ti*® software by assigning codes that categorize views, themes, and opinions, rely on constant comparative analysis⁹⁹ and a phenomenological approach.^{100,101} In the pilot field trial, the primary outcome is change in sun protection pre to post, analyzed with a paired t-test; changes in perceived risk, response- and self-efficacy, and sunburn will be compared pre to post, similarly. Message recall (i.e. receipt of the messages), users' reactions, barriers, and willingness to use *SS*, will be summarized as proportions/means and compared on demographics (including if treatment differs as a function of biological sex), using chi-square tests, t-tests, and correlations at $p=0.05$ (2-tailed). We will likewise test if *SS* messages (message recall) reduced physical activity (IPAQ). Recruitment rates and duration, and follow-up rates, will be described to plan a future randomized trial on *SS*. Data will be de-identified and stored in KB's secure servers. [name] will oversee data analysis. SAS will be used for analyses.

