Focus groups will be recorded, transcribed, and analyzed using Atlas-ti[©] software by assigning codes that categorize views, themes, and opinions, rely on constant comparative analysis and a phenomenological approach. In the pilot field trial, primary outcome is change in sun protection pre to post, analyzed with a paired t-test; changes in perceived risk, response- and self-efficacy, and sunburn will be compared pre to post, similarly. Message recall (i.e. receipt of the messages), users' reactions, barriers, and willingness to use SS, will be summarized as proportions/means and compared on demographics, using chi-square tests, t-tests, and correlations at $p=0.05$ (2-tailed). Power analysis was estimated using treatment effect sizes from our sunZapp trials. For this small-scale pilot test, we powered on the quasi-experimental pretest-posttest comparison within the SS group, using a paired samples t-test. Assuming an effect size of 0.23 in sun protection pre to post and a correlation between the pre/post scores of 0.5, we will need 181 participants with complete pre-post data to detect an effect of this size with power of 0.80 in a 2-tailed $p=0.05$ test, which we factored up to 226 to account for 20% attrition. Recruitment rates and duration, and follow-up rates, will be described for planning a future randomized trial on SS effectiveness. We will test if sun safety messages (SS message recall) reduced physical activity (IPAQ), using correlations. The control group sample is not designed to test for statistical differences in comparison to the treatment group. Data will be de-identified and stored in KB's secure servers. [name] will oversee data management and analysis. SAS will be used for analyses.

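### The pilot is said to test whether Strava Sun improves sun protection, but the only planned analysis is a before-after paired t-test, with no estimate against the randomised controls

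*Combined protocol and SAP*

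**What the plan says.** Section 3C.1 (Project Overview and Timeline) concedes that many aims concern feasibility, then gives the pilot an effect hypothesis: "establish methodologic feasibility, analysis of the pilot field trial in Months 22-24 will test the hypothesis that SS will improve sun protection".

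The analysis does not follow from that. The Statistical Analysis Plan says the "primary outcome is change in sun protection pre to post, analyzed with a paired t-test", and section 3C.7 says the same. Perceived risk, efficacy beliefs and sunburn are to be handled in the same way. The analysis sentence does not say which arm enters the t-test. The power text (3C.6 and the SAP) places it within the SS group and calls it quasi-experimental.

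Section 3C.6 describes a randomised, controlled pretest-posttest design with 3.5:1 allocation to SS or an untreated control. The arm sizes are 176 and 50 (Protection of Human Subjects, item 4). Both arms are followed up: "All participants will complete posttest survey 4 months after randomization". Controls are paid for both surveys. Section 3C.6, item 4 of Protection of Human Subjects and the SAP all say the control group is not meant for statistical comparison. The first two give its purpose as judging whether a no-treatment control is acceptable and estimating follow-up. Section 2 leaves efficacy to a later randomised trial.

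**The concern.** Change in one arm over four months is the sum of any SS effect and whatever else moves the score in that time, such as season, repeated questioning and regression to the mean. A paired t-test rejects when that sum differs from zero. It does not test whether SS caused the change, which is the hypothesis in 3C.1.

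Calendar change is a credible rival explanation here. In section 3A.1 the plan ties prevention to "limiting time in the sun when UV is high (e.g., at midday; at lower latitudes; near summer solstice", so it treats UV as seasonal. Sunburn, a secondary outcome, is recalled over four months: "sunburn (defined as skin red and/or painful from exposure to the sun in the past four months". Its pretest and posttest therefore cover different parts of the year. For the sun-protection score no recall window is stated. Season sensitivity of that score is plausible but not established by the documents.

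Section 3B.1 says the findings must confirm the promise of SS before a randomised trial is funded. Read with 3C.1, a significant before-after change could be taken as evidence that SS works when part or all of it is calendar change. A shift the other way could hide a real effect.

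**Working it through.** **1. The plan's own sample size**

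Inputs (3C.6 and SAP): effect 0.23, pre/post correlation r = 0.5, two-sided 0.05, power 0.80.

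- Standardised change: 0.23 / sqrt(2(1 − 0.5)) = 0.23. With r = 0.5 the SD of change equals the SD of the score, so the units coincide.
- Normal approximation: ((1.96 + 0.8416) / 0.23)² = 148.4, so 149 pairs. The noncentral t gives 151.
- The plan states 181, which these inputs do not reproduce. It would need r of about 0.40 or a standardised change of about 0.21.
- The attrition step does reproduce: 181 / 0.80 = 226.25.

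The 226 includes the 50 controls. Assuming 20% attrition in each arm, SS completers are 176 × 0.80 ≈ 141 and control completers 50 × 0.80 = 40. Paired power at 0.23 with 141 pairs is 0.774. The 181 discrepancy is a separate matter; only 141 and 40 are carried forward.

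**2. What drift does to the paired test** (n = 141, two-sided 0.05, noncentral t; drift sizes are assumptions)

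| True SS effect (SD) | Net drift (SD) | Probability of significance |
|---|---|---|
| 0 | 0 | 0.050 |
| 0 | 0.05 | 0.091 |
| 0 | 0.10 | 0.218 |
| 0 | 0.15 | 0.424 |
| 0 | 0.20 | 0.655 |
| 0.23 | 0 | 0.774 |
| 0.23 | −0.10 | 0.335 |

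**3. Does rolling enrolment average the season out?**

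Section 3C.6 says "Participants will be enrolled on a rolling basis". The window is short on either account:

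- Section 3C.1: "In Months 16-21, feasibility of SS will be tested in a pilot field trial with Strava users". That is 6 months, less 4 months of follow-up, leaving 2.
- Section 3C.6: "Eight months are allotted for the field trial". Eight months less 4 leaves 4.

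Assume a 12-month sinusoid and uniform enrolment over W months. The mean shift, as a fraction of the largest single-participant shift, is |sin(phase)| × sin(πW/12) / (πW/12).

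| | W = 4 | W = 2 |
|---|---|---|
| Ceiling | 0.827 | 0.955 |
| Median over start dates | 0.585 | 0.675 |
| Share of start dates above half the maximum | 0.587 | 0.649 |
| Rejection with no SS effect, maximum 0.10 SD: mean (range) | 0.107 (0.050–0.164) | 0.126 (0.050–0.203) |
| Rejection with no SS effect, maximum 0.20 SD: mean (range) | 0.277 (0.050–0.496) | 0.344 (0.050–0.615) |

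Means are over all start dates, because no calendar dates are given. Enrolment over 2 or 4 months cannot be relied on to cancel a seasonal shift.

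**4. What the randomised contrast would give** (ANCOVA of posttest on arm and pretest)

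- SE = sqrt((1 − 0.5²)(1/141 + 1/40)) = 0.155 SD.
- 95% CI half-width 0.306 SD; power at 0.23 is 0.314.
- An observed 0.23 would give about −0.08 to 0.54.
- If r is 0.3 or 0.7: half-width 0.34 or 0.25, power 0.27 or 0.43.
- With 30 control completers (r = 0.5): SE 0.174, half-width 0.344, power 0.259.

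**The case against.** The strongest reply is that the omission is deliberate and disclosed. The plan says repeatedly that the controls are not for statistical comparison, calls the powered comparison quasi-experimental, and defers efficacy to a later trial. The SAP does not repeat the hypothesis in 3C.1. On this view the defect is one over-strong sentence, and rewording it would be enough. This stands as an explanation of why there is no powered between-arm test. It does not make a one-arm change answer the hypothesis that 3C.1 still states, and it does not rule out an estimate with a CI.

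Second, the documents give no drift size, direction or start date, and do not show that the primary score is seasonal. That is correct. The figures in steps 2 and 3 show sensitivity and do not predict what will happen. Nor is the paired test itself in error when scores drift, since mean change then really is non-zero. The error lies in reading that change as an SS effect.

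Third, the between-arm interval is wider than the planning effect, so it cannot separate 0.23 from zero. That also stands and limits the estimate to planning use. The contrast would still cancel, in expectation, change common to both arms, which the paired test cannot do.

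Last, no explicit go/no-go rule ties the future trial to this t-test. The influence on that decision is inferred from 3B.1.

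**Conclusion.** The concern holds and should be fixed. The hypothesis in 3C.1 is not tested by the only analysis planned for sun protection, and randomised control data that bear on it have no planned use for that outcome. Confidence is high on the mismatch, which rests on the text alone. It is lower on the size of the seasonal effect, which the documents do not establish. The illustrated 22% and 65% rejection rates, and the fall in power from 0.77 to 0.34 under an opposing 0.10 SD drift, assume r = 0.5, 20% attrition in each arm and the stated drifts.

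**What to change.** Keep the paired t-test as the powered before-after analysis, and make these additions:

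1. Report the SS-minus-control difference from an ANCOVA of posttest score on arm and pretest score, with a 95% CI. For sunburn, use a count or logistic model with arm and pretest value, according to how the item is coded.
2. Label these as planning estimates and not powered tests, and report follow-up by arm beside them.
3. State in the SAP that the paired test describes change in the SS arm and does not by itself show that SS improves sun protection.
4. Reword the hypothesis sentence in 3C.1 to agree with section 2, section 3C.6 and the SAP.

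The cost is one added model for each outcome concerned and two wording changes, with no new participants or data. The drawbacks should be stated. The interval is wide, and self-report against an untreated control can favour SS. Survey payments differ by arm: SS USD 65 in 3C.6 and in item 4 of Protection of Human Subjects, but USD 75 in the Recruitment and Retention Plan; control USD 45. Unequal payment could cause differential follow-up, which the randomised contrast does not correct.

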Participation will be voluntary, with the right to stop participating at any time. No clinical data will be captured. Responses to survey questions and the discussions would not reasonably place the participants at risk of criminal or civil liability or be damaging to the participants' financial standing, employability, or reputation. All data coding, data entry, analysis and reporting activities will be conducted by KB and CSU. Participants will be informed that they have a right to withdraw from the study at any time. No additional data will be collected from participants who decide to withdraw; however, the information collected prior to withdrawal will remain in the study.

Protection Against Risk. To minimize potential psychological risk, the focus group facilitator ([name]) will establish ground rules for discussion that includes an open, non-evaluative exchange of comments and ideas. All surveys and data collection forms will be approved by WIRB and employed under the supervision of senior project staff. Participants will be told that they do not have to answer any questions which make them uncomfortable and can terminate their participation at any time they wish.

Notes, surveys, audiotapes, and data will be accessible only by research personnel. Responses to survey questions would not reasonably place the subjects at risk of criminal or civil liability or be damaging to the subjects' financial standing, employability, or reputation. No clinical data will be captured. The data collected on this project will be obtained with the "use of educational tests, survey questions, [and] interview procedures."

Data will be de-identified before being submitted for analysis. All notes and printed data collection forms and questionnaires will be stored in locked cabinets at KB offices; all electronic data files will be stored on KB's secure network servers behind computer firewalls, with routine backup. All identifiers will be stored in secure files and behind computer firewalls and results will be shared in aggregate form only. All human subjects participating in this project will be 18 years and older.

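### The primary paired t-test uses SS completers only, so the estimated change is biased if dropout depends on pretest sun protection; a likelihood model on all SS pretests removes that bias at almost no cost.

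*Combined protocol and SAP*

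**What the plan says.** Section 3C.7 and the Statistical Analysis Plan name the same primary analysis: the "primary outcome is change in sun protection pre to post, analyzed with a paired t-test". The sample-size text makes clear that the test is meant for the treated arm alone: "we powered on the quasi-experimental pretest-posttest comparison within the SS group, using a paired samples t-test". It also makes clear that only people with both scores count: "we will need 181 participants with complete pre-post data". That number is then raised to 226 for 20% attrition.

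The pretest is completed at entry, after consent, and there is one posttest, 4 months after randomisation (section 3C.6). For people who withdraw, the section on informed consent states that "the information collected prior to withdrawal will remain in the study". Their pretest scores are therefore in the database.

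Neither section 3C.7 nor the Statistical Analysis Plan gives a missing-data method, a model for incomplete pairs, a sensitivity analysis or a comparison of completers with non-completers. Follow-up rates are to be described, for planning a later trial.

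**The concern.** When pretest and posttest are imperfectly correlated, people who start low tend to rise and people who start high tend to fall, whatever the intervention does. If those who leave differ from those who stay on the pretest, the stayers' mean change carries part of this regression to the mean. It is then the wrong estimate for the SS group, even though the variable that drives the dropout has been measured.

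This is the pilot's one powered hypothesis test, and its result is meant to inform whether a randomised trial follows. Depending on who leaves, the bias could hide a real change or create an apparent one.

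**Working it through.** **Inputs from the documents.** Effect: "Assuming an effect size of 0.23 in sun protection pre to post". Correlation: "a correlation between the pre/post scores of 0.5". Power 0.80, two-sided 0.05. Attrition 20%. SS group 176 (human-subjects section, Pilot Field Testers; 226 × 3.5/4.5 = 175.8).

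**Assumed, because the documents do not give them.** The pretest gap between completers and dropouts (varied below), equal SDs at pretest and posttest, and the 20% attrition applying to the SS arm.

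**Step 1: the plan's own figure.** The SD of change, in score SDs, is √(2(1 − r)) = √(2 × 0.5) = 1, so 0.23 is the same in either unit. The required number of pairs is (1.960 + 0.842)²/0.23² = 148.4, so 149, or 151 with the t distribution. The stated 181 does not follow from the stated inputs. The step from 181 to 226 does: 181/0.8 = 226.25. That discrepancy is a separate matter; the calculation below uses the numbers that would actually be analysed.

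**Step 2: who is analysed.** 176 × 0.8 = 140.8, so about 141 pairs. About 35 SS participants with a pretest are left out.

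**Step 3: the bias.** Write q for the dropout share and g for the gap (completers' mean pretest minus dropouts'). Completers exceed the whole arm at pretest by q × g. With equal SDs the slope of posttest on pretest is r, so the slope of change on pretest is r − 1. Hence

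bias = (r − 1) × q × g.

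| r | g (SD) | bias (SD) | share of 0.23 |
|---|---|---|---|
| 0.5 | 0 | 0 | 0% |
| 0.5 | 0.25 | −0.5 × 0.2 × 0.25 = −0.025 | 11% |
| 0.5 | 0.5 | −0.5 × 0.2 × 0.5 = −0.05 | 22% |
| 0.5 | 1.0 | −0.5 × 0.2 × 1.0 = −0.10 | 43% |
| 0.3 | 0.5 | −0.7 × 0.2 × 0.5 = −0.07 | 30% |
| 0.7 | 0.5 | −0.3 × 0.2 × 0.5 = −0.03 | 13% |

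The sign reverses if high scorers leave.

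**Step 4: effect on the test (g = 0.5, r = 0.5).** The standard error is 1/√141 = 0.084.

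- True change 0.23, low scorers leave: the expected estimate is 0.18. Power ≈ Φ(0.18/0.0842 − 1.96) = Φ(0.18) = 0.57.
- True change zero, low scorers leave: the shift is 0.05/0.0842 = 0.59 standard errors downward. Rejection for harm ≈ Φ(−1.96 + 0.59) = 0.086; for benefit ≈ Φ(−1.96 − 0.59) = 0.005. The two-sided total is about 0.09.
- True change zero, high scorers leave: the two tails swap, so false benefit is about 0.087 by simulation, against a nominal 0.025.

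**Step 5: simulation** (bivariate normal scores, logistic dropout on pretest, 20% missing, 176 in SS). The likelihood analysis uses every SS pretest.

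| Dropout pattern | Paired t: estimate, power | Likelihood: estimate, power |
|---|---|---|
| Unrelated to pretest | 0.23, 0.77 | 0.23, 0.79 |
| Dropouts about 0.5 SD lower | 0.18, 0.57 | 0.23, 0.79 |
| Dropouts about 0.5 SD higher | 0.28, 0.91 | 0.23, 0.79 |

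The 0.91 in the last row reflects upward bias and is no gain. Under no change, with the 0.5 SD gap in either direction, the likelihood test rejects about 5% of the time and the paired t-test about 9%.

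**The case against.** The strongest reply is that nothing in the documents says dropout will depend on pretest score. They give no dropout pattern and no gap between completers and dropouts. Both surveys are paid, the posttest more than the pretest, and reminders and help with barriers are planned. Loss of interest in the messages is also a reaction to SS, which is not the same as a low pretest score. This stands: the size of the bias rests on an assumed gap, and at 0.25 SD it is only 0.025 SD, with power of 0.68.

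A second reply is that this is a feasibility pilot with an uncontrolled before-after comparison. Enrolment is rolling and the surveys are 4 months apart, so season and repeated surveying also enter the change, and neither analysis removes them. That limits the importance of the point. It is no reason to keep an avoidable bias.

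Three stronger readings are tempting, and the documents do not support them.

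- *The paired t-test inflates false claims that SS works.* If low scorers leave, the excess rejection lies almost wholly in the harm direction, and false benefit falls below 0.025. False benefit rises only if high scorers leave more, and the documents give no reason to expect that.
- *The model should take everyone randomised.* The plan's contrast is within SS, and it says the 50 controls are not there for testing. A model with only a time effect on all 226 would average treated and untreated change. If controls do not change (an assumption), it estimates 176/226 × 0.23 = 0.18, an error as large as the one being repaired.
- *Using all pretests solves the missing-data problem.* It deals only with dropout that depends on the observed pretest.

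**Conclusion.** The point holds as a conditional one. The primary test leaves out the pretests of about 35 of 176 SS participants, and the plan has no protection if those people differ at pretest. At r = 0.5, equal SDs and 20% attrition, the bias is 0.10 SD per SD of pretest gap, and zero with no gap. In the direction that seems more natural for a messaging trial, low scorers leaving, the cost is an understated change and lost power; it is not a false finding of benefit.

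A reader might infer that the trial's result will be biased. The documents do not show that; they show only that the named analysis cannot guard against it. The case for change rests on cost: the likelihood model loses nothing when dropout is unrelated to pretest (power 0.79 against 0.77). The gain is mainly in bias; the gain in precision is small.

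**What to change.** In section 3C.7 and the Statistical Analysis Plan:

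1. Make the primary analysis a likelihood-based repeated-measures model (SAS PROC MIXED, unstructured covariance, time effect) on all participants randomised to SS who have a pretest. Exclude controls from this contrast.
2. Keep the paired t-test on SS completers as a sensitivity analysis.
3. Report pretest scores of SS completers and non-completers side by side, so that readers can see the actual gap and apply the bias formula.
4. State that the model removes bias only from dropout that depends on the observed pretest, and not from dropout driven by the unseen posttest or by reaction to the messages.

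The cost is a few sentences in the plan and a few lines in the software already named. No extra data, participants or visits are needed.
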